The safety and effectiveness information (medical interview, telephone, etc.) will be monitored within the scope of routine clinical practice.

3) At the end of the observation period of enrolled patients, the investigator will enter the obtained information into the EDC system to transmit. The personal information, such as the name, address, date of birth, medical record number, initials of patients, must not be entered into the EDC system.

8. Study Items

The investigator will collect the information about the following items, etc. according to the following schedule as far as possible and enter it into the EDC system within the scope of routine clinical practice.

1. Study schedule

The timings of when to observe/assess the main study items are as follows.

Study	4 weeks prior	Day 1	-	Day 15	Day 22	Day 29
Study item	to administration	If inpatients have been discharged/transferred from hospital before Day 29, they will be observed until the discharge/transfer date. For outpatients, the observation will be conducted on Day 1 only.				
Patient characteristics		•				
Variant test		•				
Vaccination status against SARS-CoV-2 infection		•				
Administration status of Xevudy		•				
Pre-treatment medications	← →					
Concomitant medications						→
Combination therapies for exacerbation of SARS- CoV-2 infection ^{1, 3}						
Admission into HCU or ICU ³		←				→
Vital ^{2, 3}					•	•
Clinical symptoms ³	[←────		┝───	•	•
Status at the end of the observation		→ → → → → → → → → → → → → → → → → → →				
Pregnancy/Breastfeeding						→
AEs		←────				→

1: Invasive mechanical ventilation (IMV) management, extracorporeal membrane oxygenation (ECMO), oxygen administration (OA), etc.

2: Body temperature, percutaneous oxygen saturation (SpO2), if measured.

3: Inpatient only.

- 2. Study items
- 1. Information about a medical institution Name of a medical institution, department, investigator

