Whether or not combination therapies for exacerbation of SARS-CoV-2 infection are introduced, name of therapies (invasive mechanical ventilation (IMV) management, extracorporeal membrane oxygenation (ECMO), OA, etc.), name of therapies and date of combination therapies introduced, oxygen flow rate (maximum flow rate during the observation period) (L/min) and date of maximum flow rate introduced

<Inpatient only> Vital signs
 Highest body temperature (°C) and lowest percutaneous oxygen saturation (SpO₂) (%) and
 date of measurement at Day 1, Days 2-15 (every day), Day 22, Day 29 and the
 discharge/transfer date. On Day 1, the highest body temperature and the lowest SpO₂ will be
 selected from values which are measured before Day 1.

¹ See Guidelines for Diagnosing Patients with Novel Coronavirus Infection (COVID-19) (Guidelines Review Committee).

9. <Inpatient only> Clinical symptoms (cough without sputum (nonproductive cough), cough with sputum (productive cough), fatigue, dysgeusia, olfactory dysfunction, headache, dyspnea, sore throat, diarrhea, nasal discharge, arthralgia/myalgia), symptom of pneumonia Presence or absence of clinical symptoms and date of observation at Day 1, Days 2-15 (every day), Day 22, Day 29 and the discharge/transfer date. If any of these clinical symptoms have been identified at the date of each observation, select the clinical symptoms applicable to these.

If a symptom is not identified at Day 1 but newly occurs after Day 1 or a symptom is identified at Day 1, disappears after Day 1 and reoccurs, the symptom should be recorded into adverse events (AEs) section of the case report form (CRF) in case where it is assessed as an AE.

10.<Inpatient only> Admission status into high care unit (HCU) or intensive care unit (ICU) during observation period

Whether or not a patient is admitted into HCU or ICU and date of admission

11.Status at the end of the observation

End date of observation, inpatient outcome (hospitalization, discharge, transfer, and the reason), and whether or not a patient has died from exacerbation of SARS-CoV-2 infection and the reason

12.Pregnancy

(For female patients) whether or not a patient is pregnant during the observation period, estimated delivery date

In addition, the follow-up investigation should be conducted for a mother and her foetus as far as possible regarding the course of delivery, spontaneous abortion, elective abortion, and AEs, etc.

13.Breastfeeding

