Among the patients who can be assessed for the following items a) to e) from Day 1 to the end of observation period, the following patients will be defined as "not effective" if applicable to any of a) to e). The proportion of non-responders is the proportion of patients assessed as "not effective" in the clinical outcomes analysis set.

- a) Patients who receive oxygen at a rate of <5L/min as a combination therapy for exacerbation of SARS-CoV-2 infection
- b) Patients who receive any of the following combination therapies for exacerbation of SARS-CoV-2 infection
 - Non-invasive positive pressure ventilation (NPPV)
 - Invasive mechanical ventilation (IMV) management
 - Extracorporeal membrane oxygenation (ECMO)
- c) Patients who require admission to HCU or ICU for exacerbation of SARS-CoV-2 infection in medical institutions with HCU or ICU
- d) Patients who are transferred to another hospital for exacerbation of SARS-CoV-2 infection to receive the treatments of a) to c) mentioned above
- e) Patients who result in death for exacerbation of SARS-CoV-2 infection
- ii) <Inpatient only> Distribution and transition of vital signs (Day 1, Days 2-15, Day 22, Day 29, discharge/transfer date)
- iii) <Inpatient only> Distribution and transition of clinical symptoms (Day 1, Days 2-15, Day 22, Day 29, discharge/transfer date)
- 2. Analysis methods
 - 1) Safety
 - i). The incidence rate of ADR patients will be calculated throughout the whole period, at Day 1, Days 2-15, Day 22, Day 29.
 - ii). The incidence rate of ADR-experiencing patients per 100 patient-years will be calculated along with 95% exact Poisson confidence intervals using chi-square distribution.
 - 2) Clinical outcomes

- i) The proportion of non-responders will be calculated (from Day 1 to the end of the observation period). The proportion of non-responders by sampling period for nucleic acid detection tests/antigen tests showing positive will be calculated.
- ii) The proportion of patient outcome at the end of the observation period in patients other than non-responders was be calculated.
- Summary statistics for vital signs will be calculated based on values at the time of measurement (Day 1, Days 2-15, Day 22, Day 29, discharge/transfer date). Also, summary statistics for vital signs by sampling period for nucleic acid detection tests/antigen tests showing positive will be calculated.

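### Non-response component c) depends on why a patient entered HCU or ICU, but the listed data item records only whether and when

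*Protocol*

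**What the plan says.** Section 9 (Analysis items, Clinical outcomes) classes an inpatient as a non-responder if any one of five components, a) to e), applies. Component c) reads: "Patients who require admission to HCU or ICU for exacerbation of SARS-CoV-2 infection in medical institutions with HCU or ICU". It has two conditions: the admission is for exacerbation, and the institution has such a unit.

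Section 8, Study items, lists what is collected. Item 10 is the only item on HCU or ICU admission: "Whether or not a patient is admitted into HCU or ICU and date of admission". The schedule table adds the timing and the restriction to inpatients, nothing more.

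The items behind the other components are worded differently. Item 7 asks "Whether or not combination therapies for exacerbation of SARS-CoV-2 infection are introduced". Item 11 asks for "inpatient outcome (hospitalization, discharge, transfer, and the reason" and for "whether or not a patient has died from exacerbation of SARS-CoV-2 infection and the reason". The list as a whole is introduced by "The investigator will collect the information about the following items, etc", so it is not strictly closed, and the CRF is a separate attachment.

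**The concern.** The endpoint rule needs the cause of an admission, and the data item holds only the event. A statistical analysis plan can set rules for data that exist, but it cannot supply a reason that nobody recorded. If the list is followed as written, the analyst must count every admission, count none, or infer the cause from other fields.

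Other causes are plausible in this population. Patients are enrolled because they have risk factors for severe disease, and their comorbidities are recorded. One possible cause is the study's own safety concern: a patient moved to intensive care for anaphylaxis or an infusion reaction would be scored as a failure of effectiveness if all admissions count.

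Three outputs depend on the classification: the non-responder proportion (including its breakdown by sampling period), the modified Poisson regression for risk factors of non-response, and the table of end-of-observation outcomes in patients other than non-responders. In the regression, an admission caused by a comorbidity but scored as non-response would link the outcome to that comorbidity, if it is among the factors examined.

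**Working it through.** The protocol has no figure to reproduce here. The check sets the definition against the data list.

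| Component (section 9) | Needs attribution to exacerbation? | Listed item (section 8) | Attribution or reason listed? |
|---|---|---|---|
| a) oxygen below 5 L/min | yes | item 7 | yes, therapies are recorded as given for exacerbation |
| b) NPPV, IMV or ECMO | yes | item 7 | yes, same item |
| c) HCU or ICU admission | yes | item 10 | **no**, only yes/no and date |
| d) transfer | yes | item 11 | yes, a reason is recorded with the outcome |
| e) death | yes | item 11 | yes, asked as death from exacerbation |

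Only c) lacks it.

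**Who is affected.** Any one component is enough, so patients who already meet a), b), d) or e) are classified correctly whatever item 10 holds. Let N be the patients in the analysis and A the number meeting at least one of a), b), d), e). Among the remaining patients, let k be those admitted to HCU or ICU for exacerbation and m those admitted only for another reason.

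- By the definition: proportion = (A + k) / N.
- Counting every admission: (A + k + m) / N. Error = +m / N, which is zero or positive.
- Counting no admission under c): A / N. Error = −k / N, which is zero or negative.

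The listed items give k + m but not the split.

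**Is k likely to be empty?** Not by construction. As worded, a) covers oxygen below 5 L/min and b) covers NPPV, IMV and ECMO. A patient given oxygen only at a higher flow meets neither, so c) may be the only component that classifies that patient.

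**Size.** The protocol gives no m, no k and no number of inpatients. Each misclassified patient shifts the proportion by 1/N. If all 630 planned patients were inpatients, that is 1/630 = 0.16 percentage points; with an assumed 300 inpatients it is 1/300 = 0.33 points. How many such patients there would be is unknown, so no total follows.

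**The institution condition.** A recorded admission to a unit at the site shows that the site has one, so the numerator of c) needs no extra field. The condition could matter for who counts as assessable, but item 1 records "Name of a medical institution, department, investigator", and about 30 institutions are planned, so availability can be established per site.

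**The case against.** The strongest objection is that the CRF is not shown and the item list is open-ended, so a reason field may already exist. This stands as a limit. A reader might infer that c) cannot be derived at all, and the protocol does not support that. It supports only that item 10 does not list what c) requires.

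Second, other items can inform the cause: dated therapies for exacerbation (item 7), daily lowest SpO₂ to Day 15 (item 8), symptoms including pneumonia (item 9), reasons for concomitant medications (item 6) and dated adverse events (item 14). An unexpected worsening of a comorbidity counts as an adverse event, so an admission for it should often leave a trace. This stands in part. Patients with item 7 therapies mostly meet a) or b) already, so that item helps least where c) decides alone. Expected progression of the target disease is not an adverse event under the protocol's annex, and a precautionary admission for monitoring need leave no record either. Indirect inference therefore settles some cases, not all.

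Third, non-response is a secondary, inpatient-only endpoint in an uncontrolled surveillance study, and it is not the only effectiveness proportion: symptom proportions and end-of-observation outcomes are also planned. This is correct and limits the weight of the point.

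**Conclusion.** The mismatch is real and lies within the protocol itself. From the listed items, c) cannot be reliably derived for inpatients admitted to HCU or ICU who meet none of a), b), d) or e). Counting all admissions biases the non-responder proportion in one direction only, upward or not at all.

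A reader might want to attach a percentage error to this. The documents do not allow it: any such figure would come from an assumed number of inpatients, an assumed number of admissions for other reasons and an assumed true proportion. A reader might also infer that a missing record of whether the site has a unit is a second defect of similar weight; it is not, because an admission at the site already shows that the unit exists.

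The conclusion assumes that the CRF follows item 10 as listed. If the CRF already asks for the reason, only the protocol wording needs aligning. The primary ADR endpoint and the sample-size rationale are unaffected.

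**What to change.** Add to item 10 the reason for HCU or ICU admission, with two options: exacerbation of SARS-CoV-2 infection, or other. Add the same field to the CRF if it is not already there. Query the sites for admissions already entered, and count only those for exacerbation in c). No separate institution field is needed for the numerator.

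The cost is one extra CRF field and a few queries, with no added patient procedure. Version 3.0 is dated 26 October 2022 and scheduled enrolment runs to June 2023, so the change could be made while patients were still being entered.

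### As printed, the non-responder rule counts oxygen below 5 L/min but has no item for oxygen at 5 L/min or more, so an inpatient with greater oxygen need can go uncounted

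*Protocol*

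**What the plan says.** Protocol section 9, Analysis items, 3) i) defines non-response for inpatients. Meeting any one of five criteria is enough:

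- a) oxygen, worded as "Patients who receive oxygen at a rate of <5L/min as a combination therapy for exacerbation of SARS-CoV-2 infection", which is the only item that names oxygen
- b) ventilatory or extracorporeal support, as a closed list of three: NPPV, IMV and ECMO
- c) HCU or ICU admission because of exacerbation, counted only where the institution has such a unit
- d) transfer, worded as "Patients who are transferred to another hospital for exacerbation of SARS-CoV-2 infection to receive the treatments of a) to c) mentioned above", which makes it depend on the items before it
- e) a fatal outcome attributed to exacerbation

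The proportion is taken over the clinical outcomes analysis set. Section 9, Analysis methods, 2) then describes the end-of-observation outcome in everyone who is not a non-responder. Section 9, Analysis methods, 3) uses the proportion of non-responders as the clinical outcome in the modified Poisson risk-factor model.

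Section 8, Study items, item 7 says what is recorded about oxygen: whether a therapy was introduced, its name and date, "oxygen flow rate (maximum flow rate during the observation period"), and the date of that maximum. Section 3 restricts entry to patients who do not need oxygen for SARS-CoV-2 infection when Xevudy is given.

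**The concern.** Every patient starts without needing oxygen for the infection, so any later oxygen for exacerbation is a worsening. A rule for failure should not stop counting a patient because the worsening is greater. As printed, criterion a) has an upper limit on flow and no other criterion picks up above it. Criterion d) refers back to a) to c), so a transfer to receive oxygen at 5 L/min or more, with none of the other treatments, falls through as well.

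Missed patients stay in the denominator and are described with those who are not non-responders. The outcome concerned is a secondary endpoint in section 1, is also tabulated by sampling period of the positive test, and is one of the two outcomes examined for risk factors.

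**Working it through.** **Step 1. Map oxygen states to the criteria.** Take a patient for whom b), c), d) and e) are all absent and ask whether a) applies. The wording of a) allows two readings: the recorded maximum flow is below 5 L/min, or the patient received a flow below 5 L/min at any time.

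| Maximum flow (L/min) | a) on recorded maximum | a) as ever below 5, titrated up from below 5 | a) as ever below 5, started at the maximum |
|---|---|---|---|
| 0 | no | no | no |
| 1 | yes | yes | yes |
| 4.9 | yes | yes | yes |
| 5, 6, 10, 15, 40 | **no** | yes | **no** |

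On the maximum-flow reading the classification goes no, yes, no as flow rises. On the ever-below-5 reading, the patient titrated upwards is counted, but one who starts at 5 L/min or more and never receives less is not. That last patient is missed on both readings.

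**Step 2. Can the listed data separate the last two columns?** Section 8 lists the maximum flow, its date, and the date each therapy was introduced. A maximum of 8 L/min does not show whether the patient was ever below 5. If the introduction date is earlier than the date of the maximum, the flow rose, but the starting flow is still unknown. So the more generous reading of a) cannot be applied from these items. The maximum does, however, identify every patient who reached 5 L/min or more.

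**Step 3. Effect on the proportion.** The protocol gives no oxygen rates, so these inputs are assumptions. Per 100 assessable inpatients, let 10 receive oxygen for exacerbation, and let all non-response lie within those 10. Let a share *m* of them reach 5 L/min or more, meet none of b) to e), and go uncounted. The count is 10 × (1 − *m*):

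- *m* = 10%: 10 × 0.90 = 9
- *m* = 25%: 10 × 0.75 = 7.5
- *m* = 50%: 10 × 0.50 = 5

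If all oxygen for exacerbation counted, the figure would be 10. The relative loss equals *m*, so this shows the mechanism and does not estimate its size.

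**Step 4. Effect on risk ratios.** With missed shares *m*₁ (exposed) and *m*₀ (unexposed), the observed risk ratio is the true one × (1 − *m*₁)/(1 − *m*₀). On assumed rates:

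- True 20% v 10%, 25% missed in both: 15/7.5 = 2.0, no distortion.
- True 20% v 10%, 40% v 25% missed: 12/7.5 = 1.6, attenuated but still above 1.
- True 12% v 12%, 40% v 10% missed: 7.2/10.8 = 0.67, a spurious protective effect.

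In the 20% v 10% case with 25% missed among the unexposed, the ratio falls below 1 only when 20 × (1 − *m*₁) < 7.5, that is, when *m*₁ exceeds 62.5%.

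**The case against.** **The sign may be a misprint.** The gap rests on one character in machine-read text. If the intended wording is 5 L/min or more, the inversion disappears and what remains is a choice of threshold. This is a fair reason not to presume the sponsor's intent. It does not rescue the printed rule: whether the upper range was forgotten or the sign reversed, oxygen at 5 L/min or more would belong among the non-responders, and the text does not put it there.

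**Sicker patients may be caught elsewhere.** Many patients at high flow may meet b) to e). That stands, and it limits the claim to what can happen. Criterion c) helps only at institutions that have an HCU or ICU.

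**The outcome is secondary and exploratory.** The primary endpoint is adverse drug reactions, and the sample size rests on hypersensitivity. Neither is touched.

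A reader might also infer more than the protocol supports:

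- *That any factor driving severe oxygen need will look protective.* Step 4 shows that this needs a differential missed share, and a large one to reverse a real effect.
- *That a patient titrated up through low flow fails a).* Literally that patient meets it; the difficulty is that the listed data cannot show it. The case report form itself is an attachment that is not shown.
- *That worse patients are labelled treatment successes.* The protocol has no such category; they fall in the group other than non-responders. Nor does it rank this endpoint above the other secondary ones.

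The definition is fixed in the protocol, so this is not a detail left to the analysis plan.

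**Conclusion.** The point holds as a defect in the stated rule. An inpatient on oxygen at 5 L/min or more for exacerbation, with no NPPV, IMV, ECMO, HCU/ICU admission, qualifying transfer or death, can be left out of the non-responders while a patient on less oxygen is counted. If oxygen was started at 5 L/min or more and never went lower, the patient is missed on any reading of a).

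The direction for the proportion is certain: it can be understated and cannot be overstated by this gap. The direction for a risk ratio is not, since it depends on whether the missed share differs between factor levels. The size of either effect cannot be derived from the protocol, and the percentages above are assumptions. The consequence is confined to a secondary, inpatient-only endpoint and the exploratory model built on it, but it is cheap to remove and should be settled before the final analysis.

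**What to change.** 1. Confirm the intended threshold in a) and the direction of the sign.
2. Restate a) so that oxygen at 5 L/min or more for exacerbation counts as non-response under either intent: any flow rate if flows below 5 were meant to be included, or 5 L/min or more if the sign is reversed.
3. Define a) on the recorded maximum flow, so that the classification can be derived from the data already listed in section 8. Criterion d) then follows without further change.
4. Show maximum flow below 5 and at 5 L/min or more as separate sub-rows, so that a reader can see the result under either definition.

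This changes how the outcome is classified, not how patients are managed. The cost is one line of wording and a reprogrammed flag, with no new data. Under section 15, Protocol revision, a change that is not minor also needs written submission to the PMDA beforehand.

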"Serious Hypersensitivity such as Anaphylaxis and Infusion Reaction" is an important identified risk on Risk Management Plan (RMP) for Xevudy. The incidence rate of patients experiencing events correspond to Hypersensitivity (narrow) in Standardised MedDRA Queries (SMQs) within Xevudy group for 29 days was 1.7% (9/523 patients) in the global phase II/III clinical study for patients with mild to moderate infections (COMET-ICE Study). A total of 600 patients as a safety analysis set is required to monitor the incidence rate of event-experiencing patients in the post-marketing surveillance (PMS), with estimation accuracy that enables a power of \geq 80 % to detect an odds ratio of 2 for the 1.7% threshold, in case where there is the twofold real risk of the threshold. Accordingly, it is thought to be possible to examine the incidence rate in the drug use investigation of 630 patients.

5. Planned Number of Medical Institutions by Department

Approximately 30 medical institutions which provide SARS-CoV-2 infection treatment, mainly medical institutions designated for infectious diseases, regional medical care support hospitals and special functioning hospitals

6. Study Period

- 1. Study conduct
- 1) Study period: November 2021 to October 2023
- 2) Observation period:

The observation period per patient will be between Day 1 to 29 counting the date of Xevudy administration as Day 1 (28 days from the day following Xevudy administration or Day 2). If inpatients have been discharged/transferred from hospital before Day 29, they will be observed until the discharge/transfer date. For outpatients, the observation will be conducted on Day 1 only.

3) Scheduled enrolment period: January 2022 to June 2023

However, if the number of enrolled patients has reached the target sample size, enrolment may be terminated even before the completion of the above-mentioned scheduled enrolment period.

 Study end Time for final analysis to complete: June 2024 Time for final report writing to complete: December 2024

7. Study Methods

In this study, an electronic data capture (EDC) system will be used to enroll patients and collect data.

- 1. Request and contract for the study
 - The medical representative (MR) will explain the objectives, target population, study items, study methods, etc. to the planned physicians for the study, etc. at the medical institutions to which Xevudy is supplied and will request them to cooperate with the study.

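### Non-response is a crude proportion observed only until discharge or transfer, so event-free inpatients transferred early for reasons other than exacerbation weigh the same as those followed to Day 29

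*Protocol*

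**What the plan says.** The proportion of non-responders is a secondary endpoint, assessed in inpatients only. The Protocol fixes it as follows.

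- **Follow-up** (Section 6, Observation period): "The observation period per patient will be between Day 1 to 29 counting the date of Xevudy administration as Day 1". However, "If inpatients have been discharged/transferred from hospital before Day 29, they will be observed until the discharge/transfer date". The early end applies to every discharge and every transfer, whatever the reason.
- **Who is assessed** (Section 9, 1. 3) i)): "Among the patients who can be assessed for the following items a) to e) from Day 1 to the end of observation period". No minimum follow-up is stated.
- **Measure** (same place): "The proportion of non-responders is the proportion of patients assessed as 'not effective' in the clinical outcomes analysis set". Time at risk does not enter.
- **Transfers** (item d)): the only kind that counts by itself is "Patients who are transferred to another hospital for exacerbation of SARS-CoV-2 infection to receive the treatments of a) to c) mentioned above".

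The measure is used in two further places. Section 9, 2. 2) i) states: "The proportion of non-responders by sampling period for nucleic acid detection tests/antigen tests showing positive will be calculated". Section 9, 2. 3) models it by robust (modified) Poisson regression to explore risk factors, with no time-at-risk term or fixed horizon mentioned.

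Two provisions bear on the remedy. Section 9, 2. 2) ii) plans an end-status table: "The proportion of patient outcome at the end of the observation period in patients other than non-responders was be calculated". Section 8, item 11 collects the end date, the inpatient outcome (including transfer) and the reason.

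**The concern.** A proportion over a 28-day window means what it appears to mean only if everyone is watched for the window, or if leaving it early tells us the outcome. Discharge home can reasonably be taken as a sign of recovery. A transfer for bed management, care of a comorbidity or rehabilitation cannot, because the later course is simply unseen. Under the stated rules that patient still fills a full place in the denominator with no event.

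Two results are at stake. The overall proportion can come out too low. Contrasts between sampling periods, or between levels of a risk factor, can also reflect how long patients were watched as well as how often they worsened. Enrolment is scheduled from January 2022 to June 2023, long enough for admission and transfer practice to change. The plan does allow for observed time elsewhere: Section 9, 2. 1) ii) gives adverse drug reactions per 100 patient-years. It has no counterpart for non-response.

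**Working it through.** **Figures in the plan.** The Protocol states none for non-response. Its one design figure, 600 patients in the safety analysis set, concerns hypersensitivity events and does not bear on this point.

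**Step 1: two patients under the rules as written.**

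| | Patient A | Patient B |
|---|---|---|
| Course | Transferred on Day 2 for bed management | In hospital to Day 29 |
| Event under a) to c) while observed | None | None |
| Item d) | Not met (not for exacerbation) | Not met |
| End of own observation | Day 2 | Day 29 |
| Contribution | Denominator only | Denominator only |

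The two count identically, with 1 and 28 days observed after the administration day.

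**Step 2: recorded proportion by days observed.** All inputs are assumptions. Let R = 10% be the 28-day risk, m the mean-onset parameter in days of an exponential onset time truncated at 28 days, and L the days observed:

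F(L) = (1 − e^(−L/m)) / (1 − e^(−28/m)), recorded = R × F(L).

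| L (days) | m = 3 | m = 5 | m = 10 |
|---|---|---|---|
| 1 | 2.8% | 1.8% | 1.0% |
| 5 | 8.1% | 6.3% | 4.2% |
| 10 | 9.6% | 8.7% | 6.7% |
| 28 | 10% | 10% | 10% |

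**Step 3: a share f moved on Day 2, all others followed to Day 29 (m = 5).** F(1) = (1 − e^(−0.2)) / (1 − e^(−5.6)) = 0.182. Recorded = 10% × [(1 − f) + f × 0.182].

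- f = 5%: 9.6%
- f = 10%: 9.2%
- f = 20%: 8.4%
- f = 30%: 7.5%

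**Step 4: two groups with the same true risk but different stays.** Apparent ratio = F(short stay) / F(long stay).

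| Stays | m = 3 | m = 5 | m = 10 |
|---|---|---|---|
| 5 v 10 days | 0.84 | 0.73 | 0.62 |
| 7 v 14 days | 0.91 | 0.80 | 0.67 |

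Steps 2 to 4 assume that leaving hospital is unrelated to risk.

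**Step 5: does reporting with and without these transfers bracket the truth?** Take f = 20% and m = 5.

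- *Equal risk (true value 10%).* Event-free transfers are 20% × (1 − 0.10 × 0.182) = 19.64% of patients. With them: 8.36%. Without them: 8.36 / (100 − 19.64) = 10.4%. The pair encloses 10%.
- *Transferred patients at twice the risk (20%).* True value = 0.8 × 10% + 0.2 × 20% = 12%. With them: 8% + 0.2 × 20% × 0.182 = 8.73%. Event-free transfers are 20% × (1 − 0.20 × 0.182) = 19.27%. Without them: 8.73 / 80.73 = 10.8%, still below 12%.

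Dropping event-free transfers removes only patients without an event, so at equal risk it overshoots. It serves as an upper limit only while transferred patients are not at clearly higher risk than the rest.

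**The case against.** The opposing case has real substance.

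- **Assessability may be left open.** The restriction to patients who can be assessed could be applied to exclude very short follow-up, and Section 9 leaves detail to a Statistical Analysis Plan that is not at hand. This stands in part. However, the Protocol itself fixes the window, the items and the denominator, and on its plain wording an early transfer is assessed to the end of that patient's own observation period.
- **Transfers will be visible.** The end-status table for the remaining patients would show how many were transferred. That is right, but no split by reason is stated, and the table corrects neither the proportion nor the risk ratios.
- **The setting is modest.** This is a descriptive secondary endpoint in routine practice, and the primary endpoint is adverse drug reactions. That limits the weight of the point.

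A reader might infer stronger things that the documents do not support:

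- *Every transfer not made for exacerbation is scored as a success.* No effective or success category is defined, and a patient who met a), b) or c) before transfer remains a non-responder.
- *The by-period result simply tracks length of stay.* The by-period proportions are only calculated, with no test stated, and there are no stay data. They are also not the plan's only view over calendar time, because vital signs and symptoms are shown by sampling period too.
- *The error is large.* A constant daily risk of 0.5% gives 1 − 0.995^4 = 2.0% over 4 days and 1 − 0.995^10 = 4.9% over 10, about 2.5-fold. This requires risk to continue unchanged after leaving, which conflicts with reading discharge as recovery. Likewise, a fall from 10% to 9.0% or 8.0% with 10% or 20% transferred is the limit in which no event precedes transfer.

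**Conclusion.** The point holds in a limited form. Event-free inpatients transferred early for reasons other than exacerbation count as not non-responders on the same footing as patients followed to Day 29. This can bias the proportion downward. The by-period proportions and the risk ratios can be distorted if observed time differs between periods or factor levels, because no common horizon or time at risk is stated. This is a consequence of a stated rule rather than of missing detail.

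The true size cannot be known from the documents. The illustrations suggest roughly one to one and a half percentage points on an assumed 10% when 10% to 20% are moved on Day 2. They suggest an apparent reduction of 16% to 38% when stays are 5 rather than 10 days. Both assume that leaving is unrelated to risk, and both shrink if patients leave because they have recovered. The change is worth making because it is cheap, but the primary safety result is not affected by it.

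**What to change.** In Protocol Section 9, using dates and reasons already collected:

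1. Show event-free inpatients transferred for reasons other than exacerbation as a separate category. Give the non-responder proportion with and without them in the denominator, as lower and upper limits. State that the upper one presumes their risk was not higher than that of the rest.
2. Overall and by sampling period, add the cumulative incidence of non-response by fixed days, for example Day 8, Day 15 and Day 29. Censor at transfer for other reasons and treat discharge as a competing event. Report the number still under observation and the median observation length alongside.
3. Label the result, including the by-period proportions and risk ratios, as in-hospital non-response up to discharge or transfer. The label is needed because step 2 does not recover worsening after discharge, so shorter stays can still lower the in-hospital figure.

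The cost is analysis wording and one more table. The introduction dates of therapies, the date of HCU or ICU admission, the end date of observation and the transfer reason are all in Section 8, so no new data are needed. The reported proportion may become slightly higher.
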